D. Inclusion Criteria for all patients:

- 3.17 Age  $\geq$ 18 years.
- 3.18 ECOG Performance Status (PS) 0 or 1 (Appendix III).
- 3.19 The following laboratory values obtained  $\leq$ 14days prior to registration.
  - Creatinine  $\leq$  1.5 X upper limit of normal (ULN) OR Creatinine Clearance  $\geq$  60 mL/min for subject with creatinine levels  $>$  1.5 X institutional ULN
  - Platelet count  $\geq$ 25 x  $10^9$ /L
  - Absolute neutrophil count  $\geq$  0.5X $10^9$ /L
  - Total bilirubin  $\leq$ 1.5 x upper limit of normal (ULN) unless due to Gilbert's disease. If total bilirubin is  $>$ 1.5 x ULN, a direct bilirubin should be performed and must be  $\leq$  upper limit of normal
  - AST (SGOT) or ALT (SGPT)  $\leq$  2.5 X ULN
- 3.19a Negative pregnancy test done  $\leq$ 7 days prior to registration, for women of childbearing potential only.
- 3.19b Provide informed written consent.
- 3.19c Willing to return to enrolling institution for follow-up (during the Active Monitoring Phase of the study).

Note: During the **Active Monitoring** Phase of a study (i.e., active treatment and observation), participants must be willing to return to the consenting institution for follow-up.

- 3.19d Willing to provide bone marrow, tissue, and blood samples for correlative research purposes (see Sections 6.2, 14.0, and 17.0).
- 3.19e Must have failed or be unable to tolerate or refused other available FDA approved effective therapies. NOTE: Patients should not have other treatment options considered curative.

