6.2 Correlative Research

A mandatory correlative research component is part of this study. The patient will be automatically registered onto this component (see Sections 3.19c, 14.0, and 17.0).

6.3 Documentation of IRB approval must be on file in the Registration Office before an investigator may register any patients.

In addition to submitting initial IRB approval documents, ongoing IRB approval documentation must be on file (no less than annually) at the Registration Office (fax: [REDACTED]). If the necessary documentation is not submitted in advance of attempting patient registration, the registration will not be accepted and the patient may not be enrolled in the protocol until the situation is resolved.

When the study has been permanently closed to patient enrollment, submission of annual IRB approvals to the Registration Office is no longer necessary.

6.4 Prior to accepting the registration, registration application will verify the following:

- IRB approval at the registering institution

- Patient eligibility
- Existence of a signed consent form
- Existence of a signed authorization for use and disclosure of protected health information

At the time of registration, the following will be recorded:

- Patient has/not given permission to store and use his/her sample(s) for future research of CLL/NHL at Mayo.
- Patient has/not given permission to store and use his/her sample(s) for future research to learn, prevent, or treat other health problems.
- Patient has/not given permission for MCCC to give his/her sample(s) to researchers at other institutions.

- 6.5 Treatment cannot begin prior to registration and must begin  $\leq$  14 days after registration.
- 6.6 Pretreatment tests/procedures (see Section 4.0) must be completed within the guidelines specified on the test schedule.
- 6.7 All required baseline symptoms (see Section 10.6) must be documented and graded.
- 6.8 Treatment on this protocol must commence at Mayo Clinic Rochester, Mayo Clinic in Florida, or Mayo Clinic in Arizona under the supervision of a Hematologist.
- 6.9a Study drug is available on site.
- 6.9b **Continuation Phase (Combination Treatment with MK-3475 and Ibrutinib/Idelalisib):** To register a patient fax [REDACTED] a completed continuation phase eligibility checklist to the Registration Office between 8 a.m. and 4:30 p.m. central time Monday through Friday.

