**NOTES:**

- In case toxicity does not resolve to Grade 0-1 or baseline within 8 weeks after last infusion, trial treatment should be discontinued after consultation with the study chair. With study chair and Sponsor agreement, subjects with a laboratory or non-significant adverse event still at Grade 2 or baseline after 8 weeks may continue treatment in the trial only if asymptomatic and controlled with appropriate supportive care.
- Subjects who experience a recurrence of the same severe or life-threatening event at the same grade or greater with re-challenge of MK-3475 should be discontinued from trial treatment.

1. Consideration should be given to MK-3475 or Idelalisib as the causative agent in the setting of enterocolitis/pneumonitis, if both agents are being utilized. Consultation with the study chair is warranted.
2. In case of autoimmune hepatitis, when grade 3 (AST or ALT >5.0 times ULN and/or total bilirubin >3.0 times ULN), discontinue MK 3475 or combination therapy. Consider appropriate consultation and liver biopsy to establish etiology of hepatic injury. If necessary, treat with high-dose intravenous or oral glucocorticosteroids (prednisone equivalent 1-2 mg/kg) for 24 to 48 hours. When symptoms improve to grade 1 or less, a steroid taper should be started and continued. If serum transaminase levels do not decrease 48 hours after initiation of systemic steroids, oral mycophenolate mofetil 500 mg every 12 hours may be given.

**MK-3475 will be withheld for drug-related Grade 4 hematologic toxicities per table in 8.4, non-hematological toxicity  $\geq$  Grade 3 including uncontrolled laboratory abnormalities, and severe or life-threatening AEs as per Tables in 8.3 and 8.4**

8.4 MK-3475 Dose Modification for Hematological Toxicities (Platelet and Hemoglobin only) for MK-3475.

Note: hematological toxicity is not based on CTCAE 4.0 except neutrophil, but based on CLL specific hematological toxicity (this table and Appendix IV).

Dose modification guidelines for drug-related hematological (hemoglobin and platelets) adverse events

Toxicity	Grade 	Decrease from pretreatment 	Hold Treatment (Y/N)	Timing for restarting treatment	Dose/Schedule for restarting treatment	Discontinue Subject (after consultation with PI)
CLL/NHL specific Hematological 1 Toxicity (appendix IV)	1	11-24% decrease in HGB or PLT	No	N/A	N/A	N/A
	2	25-49% decrease in HGB or PLT				

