### 10.6 Required Routine Reporting

Adverse events to be graded at each evaluation and pretreatment symptoms/conditions to be evaluated at baseline per the CTCAE v4.0 grading unless otherwise stated in the table below:

System Organ Class (SOC)	Adverse event/Symptoms	Baseline	Each evaluation
Investigations	Platelet count decreased*	X	X
	Neutrophil count decreased	X	X
Blood and lymphatic system disorders	Anemia*	X	X
Gastrointestinal disorders	# of stools	X	
	Diarrhea		X
	Nausea	X	X
	Vomiting	X	X
Respiratory, thoracic and mediastinal disorders	Cough	X	X
	Dyspnea	X	X
	Pneumonitis	X	X
Skin and subcutaneous tissue disorders	Rash maculo-papular	X	X

\* Grading will be performed by the study statisticians at the time of analysis based on the CLL toxicity grading scale for blood counts in Appendix IV. CTCAE grades for platelet count decreased and anemia will also be recorded for reporting purposes.

10.61 Submit via appropriate MCCC Case Report Forms (i.e., paper or electronic, as applicable) the following AEs experienced by a patient and not specified in Section 10.6:

10.611 Grade 2 AEs deemed *possibly, probably, or definitely* related to the study treatment or procedure.

10.612 Grade 3 and 4 AEs regardless of attribution to the study treatment or procedure.

10.613 Grade 5 AEs (Deaths)

10.6131 Any death within 30 days of the patient's last study treatment or procedure regardless of attribution to the study treatment or procedure.

10.6132 Any death more than 30 days after the patient's last study treatment or procedure that is felt to be at least possibly treatment related must also be submitted as a Grade 5 AE, with a CTCAE type and attribution assigned.

10.62 Refer to the instructions in the Forms Packet (or electronic data entry screens, as applicable) regarding the submission of late occurring AEs following completion of the Active Monitoring Phase (i.e., compliance with Test Schedule in Section 4.0).

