16.326 Overall survival is defined as the time from registration to death due to any cause. The distribution of overall survival will be estimated using the method of Kaplan-Meier.

16.327 Arm A and Arm C: The overall response rate for the combination of MK-3475 and the signal inhibitor (targeted agents) will be estimated by the number of patients with an objective status of CR, CRi, nPR, CCR or PR (Arm A) or PMR, CMR, PR or CR (Arm C) while on the combination therapy divided by the total number of evaluable patients. All evaluable patients who receive the combination therapy will be used for this analysis. Exact binomial 95% confidence intervals for the true overall response rate to the combination will be calculated. In addition, the responders on this study will be further examined in an exploratory manner to determine if there are any patterns in prognostic factors or disease characteristics, including whether the patient had a Richter's transformation or Ibrutinib-resistant disease, for both single-agent MK-3475 and combination therapy responders.

16.328 Adverse Events: All eligible patients that have initiated treatment will be considered evaluable for assessing adverse event rate(s). The maximum grade for each type of adverse event will be recorded for each patient, and frequency tables will be reviewed to determine patterns. Additionally, the relationship of the adverse event(s) to the study treatment will be taken into consideration. Adverse events will be evaluated for single-agent MK-3475 in each arm and also for the combination of MK-3475 and the signal inhibitor in Arm A and Arm C.

16.33 Correlative Analyses:

16.331 PD-1, PD-L1 and PD-L2 will be measured for each patient at baseline and during treatment. Each measure will be summarized descriptively by median, min, max and interquartile range. Overall response and complete response will be correlated with each measure using Wilcoxon rank sum test. The relationship between each measure and time to event measures (DR, TNT, PFS) will be evaluated using Cox proportional hazard models.

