#### Appendix IV Grading Scale for Hematologic Toxicity in CLL Studies

Decrease from Pretreatment value (%)	Grade 	
	Platelets 	Hemoglobin 
No change - 10%	0	0
11-24%	1	1
25-49%	2	2
50-74%	3	3
≥ 75%	4	4

1. A decrease in circulating granulocytes is not being considered since it is not a reliable index in CLL.
2. Grades: 1–mild; 2–moderate; 3–severe; 4–life-threatening. Grade 5 (fatal) toxicity can potentially occur at any level of decrease from pretreatment values and will be recorded as such.
3. If, at any level of decrease the platelet count is  $< 20,000/\mu\text{L}$ , this will be considered grade 4, unless the initial platelet count was  $\leq 20,000 \mu\text{L}$  in which case the patient is unevaluable for toxicity referable to platelet counts.
4. Baseline and subsequent hemoglobin determinations must be immediately prior to any given transfusions.
5. If, at any level of decrease from the baseline value the platelet and/or hemoglobin counts are within normal limits, this will be considered a grade 0.

\* Hallek BD, et al.: Guidelines for the diagnosis and treatment of chronic lymphocytic leukemia: a report from the International Workshop on Chronic Lymphocytic Leukemia updating the National Cancer-Institute- Working Group 1996 guidelines: Blood 111:54465456, 2008.

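### Section 16.328 tabulates each patient's maximum adverse-event grade per treatment period without comparing it with the grade at the start of that period

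*Combined protocol and SAP*

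**What the plan says.** The rule in 16.328 is: "The maximum grade for each type of adverse event will be recorded for each patient, and frequency tables will be reviewed to determine patterns". The relationship to treatment is to be considered, without a rule for excluding events. The summary is made for the single agent in every arm and again for the combination in Arms A and C.

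Baseline grades are collected. Section 6.7 states: "All required baseline symptoms (see Section 10.6) must be documented and graded". Section 10.6 begins: "Adverse events to be graded at each evaluation and pretreatment symptoms/conditions to be evaluated at baseline". Its list has neutrophils, nausea, vomiting, cough, dyspnea, pneumonitis and rash at both baseline and each evaluation. Diarrhea is graded on study, but only a stool count is taken at baseline.

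Platelets and anemia are treated differently. The 10.6 footnote says: "Grading will be performed by the study statisticians at the time of analysis based on the CLL toxicity grading scale for blood counts". That scale, in Appendix IV, is headed "Decrease from Pretreatment value", so it already refers to baseline. Neutrophils are left off it. Note 1 of Appendix IV reads "A decrease in circulating granulocytes is not being considered since it is not a reliable index in CLL", and the note in 8.4 confirms that "hematological toxicity is not based on CTCAE 4.0 except neutrophil".

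**The concern.** Goals 2.21 and 2.24 are the safety of the single agent and of the combination. A maximum-grade table shows the total burden seen during each regimen. It does not show which events emerged or worsened in that period. Patients may enter with low counts: the 3.19 floor for "Absolute neutrophil count" is 0.5 x 10^9/L. In Arms A and C the same patient contributes to two consecutive tables, so one continuing event can appear in both. The stake is how those two descriptive tables are read. The primary response endpoint does not use them, and the DLT and stopping rules in 16.4 and 16.52 have their own criteria.

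**Working it through.** No figure in the plan rests on this rule, so there is none to reproduce. The check sets the sections side by side and then computes what can be computed.

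1. **Which entry conditions can reach the single-agent table.** Terms listed in 10.6 are graded at every evaluation, whatever their attribution. Under 10.61, an unlisted event is submitted only if it is grade 2 and at least possibly related, or grade 3 or higher. An unlisted grade 1 or unrelated grade 2 entry condition is therefore not required on the forms. Platelets and hemoglobin drop out because they are graded against the pretreatment value. Pneumonitis largely drops out because 3.27 excludes it when active and non-infectious. Diarrhea is partly protected by the stool count. That leaves mainly neutrophils, nausea, vomiting, cough, dyspnea and rash. For neutrophils, the absolute CTCAE grade is combined with a permissive entry floor. The documents do not reproduce the CTCAE cut-points, so no grade is assigned to that floor here.

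2. **What attribution does for the single agent.** Under 10.3 an entry condition can be marked unrelated, so it need not be read as drug toxicity. It still counts in the all-cause table.

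3. **What can cross the switch.** Sections 7.3 and 13.1 allow the inhibitor to be added for progression at any time, or for stable disease at month 3. Neither requires adverse events to have resolved. The continuation exclusions in 3.3 concern interacting drugs and, for idelalisib, bowel history.
   - Non-hematologic: 8.3 generally holds or stops treatment at grade 3 or higher, with restart generally at grade 0-1 or baseline, so carry-over is mainly grade 1-2. Grade 2 fatigue, for example, needs no action. As an unlisted term it is recorded only if at least possibly related.
   - Neutrophils: the hold in 8.3 is stated for grade 4 only, so up to grade 3 can be present when the inhibitor starts.
   - Attribution to study treatment cannot separate the two periods, because MK-3475 continues.

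4. **Whether an existing reset covers this.** The 16.32 heading resets disease measurements. Note 6 of the Arm A schema (note 5 for Arm C) also resets lab parameters. Footnote 4 of 8.4 resets hemoglobin and platelets for dose modification. Footnote 19 of 4.1 makes the progression visit the baseline visit for the combination, which does not clearly cover a switch for month-3 stable disease. None tells the analyst how to use a starting grade in 16.328.

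5. **Size.** For one term in one period, let b be the share of patients whose event was present at the start and is recorded again in the period, and q the share of those who worsen. Setting aside events that resolve and recur:

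   maximum-grade rate minus new-or-worse rate = b(1 - q)

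   This is zero if b = 0 or q = 1. The documents give neither b nor q.

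6. **Weight of one patient, single agent.** Sample sizes are from 16.12; the optional pooling of 9 Arm A Richter's patients into Arm C is from 16.32.
   - Arm A or B: 1/24 = 4.167% and 1/23 = 4.348%, so 4.2 to 4.3 points.
   - Arm C alone: 1/20 = 5.00% and 1/17 = 5.88%, so 5.0 to 5.9 points.
   - Arm C pooled: 20 + 9 = 29 and 17 + 9 = 26; 1/29 = 3.448% and 1/26 = 3.846%, so 3.4 to 3.8 points.

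   No combination figure is given, because the number of switchers is not in the documents.

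**The case against.** The strongest reply is that 16.328 is silent rather than wrong. It tabulates adverse events, 10.6 names pretreatment conditions separately, and the baseline grades are in the analyst's hands. Attribution is considered, goal 2.24 concerns the combination as a regimen rather than the inhibitor's increment, and nothing is decided on these tables.

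Much of this stands. The gap is an unstated derivation rule. The maximum-grade table is a legitimate summary of total burden and should stay. The 10.61 filter and the hold rules narrow what can be carried in or over, and a carried-over event that worsens is counted properly either way. What does not stand is that attribution fills the gap. It addresses cause rather than change from the starting grade, and on the combination it cannot tell a continuing MK-3475 event from one that began after the inhibitor was added.

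A reader might infer that the tables will overstate toxicity by a definite amount. The documents do not support that: any such figure needs assumed values of b and q. Nor can a combination weight be obtained by treating non-responders as the switchers. Switching is optional, and responders who progress later may also switch.

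**Conclusion.** The point holds as a limited one. Under a literal reading of 16.328, unchanged entry grades of the 10.6-listed terms count in the all-cause single-agent table. In Arms A and C, events ongoing at the switch count again in the combination table: mainly grade 1-2 for non-hematologic events, and up to grade 3 for neutrophils.

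The excess is unknown and may be zero. The one-patient weights show only how far a single case moves a rate. They assume that the denominators are the planned numbers in 16.12, with or without the optional pooling.

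A reader might extend the point to all adverse events, all blood counts or the safety stopping rules. The documents do not support this, given the 10.61 filter, the baseline-relative grading of platelets and hemoglobin, and the separate DLT definition. Only descriptive secondary safety summaries are affected.

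**What to change.** In 16.328, keep the maximum-grade table, labelled as the total burden of the regimen. Add a table of each patient's maximum grade that is new or worse than the period's own baseline:

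- Single agent: baseline is the pretreatment grade recorded under 6.7 and 10.6.
- Combination: baseline is the last adverse-event assessment and labs before the first signal-inhibitor dose, whether the switch was for progression or for month-3 stable disease.
- Use the same pre-inhibitor value for the Appendix IV grading of platelets and hemoglobin in the combination table.
- Judge diarrhea against the baseline stool count, since it has no baseline grade.
- List events ongoing at the switch separately, and count an event that resolved and recurred as new.
- State that the new table does not isolate the inhibitor's effect, because MK-3475 continues.

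This is a cheap improvement: SAP wording, one derived variable and one further table. It needs no new visits, since section 4 already schedules adverse-event assessment every cycle, at response evaluations and at progression. The downside is a second table that must be kept distinct from the first in reporting.

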**9.9b      Supportive Care Guidelines for Events of Clinical Interest and Immune-related Adverse Events (irAEs)**

Events of clinical interest of a potential immunologic etiology (irECIs) may be defined as an adverse event of unknown etiology, associated with drug exposure and is consistent with an immune phenomenon. irAEs may be predicted based on the nature of the MK-3475 compound, its mechanism of action, and reported experience with immunotherapies that have a similar mechanism of action. Special attention should be paid to AEs that may be suggestive of potential irAEs. An irAE can occur shortly after the first dose or several months after the last dose of treatment.

If an irAE is suspected, efforts should be made to rule out neoplastic, infectious, metabolic, toxin or other etiologic causes prior to labeling an adverse event as an irAE. Subjects who develop a Grade 2 or higher irAE should be discussed immediately with the Investigator/Sponsor.

Recommendations to managing irAEs not detailed elsewhere in the protocol are detailed in the table below.

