10.4 Expedited Reporting Requirements for IND/IDE Agents

Late Phase 2 and Phase 3 Studies: Expedited Reporting Requirements for Adverse Events that Occur on Studies under an IND/IDE within 30 Days of the Last Administration of the Investigational Agent/Intervention

FDA REPORTING REQUIREMENTS FOR SERIOUS ADVERSE EVENTS (21 CFR Part 312)

**NOTE:** Investigators **MUST** immediately report to the sponsor **ANY** Serious Adverse Events, whether or not they are considered related to the investigational agent(s)/intervention (21 CFR 312.64)

An adverse event is considered serious if it results in **ANY** of the following outcomes:

Death

A life-threatening adverse event

An adverse event that results in inpatient hospitalization or prolongation of existing hospitalization for ≥ 24 hours

A persistent or significant incapacity or substantial disruption of the ability to conduct normal life functions

A congenital anomaly/birth defect.

Important Medical Events (IME) that may not result in death, be life threatening, or require hospitalization may be considered serious when, based upon medical judgment, they may jeopardize the patient or subject and may require medical or surgical intervention to prevent one of the outcomes listed in this definition. (FDA, 21 CFR 312.32; ICH E2A and ICH E6).

**ALL SERIOUS** adverse events that meet the above criteria **MUST** be immediately reported to the sponsor within the timeframes detailed in the table below.

Hospitalization	Grade 1 Timeframes	Grade 2 Timeframes	Grade 3 Timeframes	Grade 4 & 5 Timeframes
Resulting in Hospitalization ≥ 24 hrs	7 Calendar Days			24-Hour 3 Calendar Days
Not resulting in Hospitalization ≥ 24 hrs	Not required		7 Calendar Days	

**NOTE:** Protocol specific exceptions to expedited reporting of serious adverse events are found in section 10.41 of the protocol.

Expedited AE reporting timelines are defined as:

“24-Hour; 3 Calendar Days” - The AE must initially be reported within 24 hours of learning of the AE, followed by a complete expedited report within 3 calendar days of the initial 24-hour report.

“7 Calendar Days” - A complete expedited report on the AE must be submitted within 7 calendar days of learning of the AE.

Serious adverse events that occur more than 30 days after the last administration of investigational agent/intervention and have an attribution of possible, probable, or definite require reporting as follows:

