16.51 The principle investigator(s) and the study statistician will review the study at least twice a year to identify accrual, adverse event, and any endpoint problems that might be developing. The Mayo Clinic Cancer Center (MCCC) Data Safety Monitoring Board (DSMB) is responsible for reviewing accrual and safety data for this trial at least twice a year, based on reports provided by the MCCC Statistical Office.

16.52 Adverse Event Stopping Rules (to be evaluated in each arm independently for single-agent MK-3475 and separately for combination therapy): The stopping rules specified below are based on the knowledge available at study development. We note that the Adverse Event Stopping Rule may be adjusted in the event of either (1) the study re-opening to accrual or (2) at any time during the conduct of the trial and in consideration of newly acquired information regarding the adverse event profile of the treatment(s) under investigation. The study team may choose to suspend accrual because of unexpected adverse event profiles that have not crossed the specified rule below.

Single-agent MK-3475: Accrual will be temporarily suspended to the affected arm if at any time we observe events considered at least possibly related to study treatment during cycles with single-agent MK-3475 (i.e. an adverse event with attribute specified as "possible," "probable," or "definite") that satisfy one of the following:

- If 4 out of the first 12 treated patients experience a DLT as defined in Section 16.4

- If after the first 12 patients have been treated, 30% of all patients experience a DLT as defined in Section 16.4.

Combination of MK-3475 and signal inhibitor (Ibrutinib or Idelalisib) in Arm A and Arm C: Initiation of treatment with the combination (addition of Ibrutinib or Idelalisib) will be halted in Arm A and Arm C if at any time we observe events considered at least possibly related to study treatment during cycles with the combination (i.e. an adverse event with attribute specified as “possible,” “probable,” or “definite”) that satisfy one of the following:

- If 2 out of the first 6 treated patients experience a DLT as defined in Section 16.4
- If after the first 6 patients have been treated, 30% of all patients experience a DLT as defined in Section 16.4.

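### The section 16.52 stopping rules tie counted events to treatment cycles and set no post-treatment window, so a late related DLT or death need not count

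*Combined protocol and SAP*

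**What the plan says.** Section 16.52 has two adverse event stopping rules.

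- **Single agent, by arm.** Accrual to the affected arm is suspended "if at any time we observe events considered at least possibly related to study treatment during cycles with single-agent MK-3475" and one of two thresholds is met: "If 4 out of the first 12 treated patients experience a DLT as defined in Section 16.4", or "If after the first 12 patients have been treated, 30% of all patients experience a DLT as defined in Section 16.4".
- **Combination, Arms A and C.** New starts of the signal inhibitor are halted on "events considered at least possibly related to study treatment during cycles with the combination", with the thresholds "If 2 out of the first 6 treated patients experience a DLT as defined in Section 16.4" and then 30% of all patients.

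Neither rule states a period after the last dose during which events still count. Four other parts of the protocol bear on this:

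- Section 9.9b: "An irAE can occur shortly after the first dose or several months after the last dose of treatment". The nursing guidelines in section 15.191 say much the same.
- Section 16.4 defines a DLT with no limit on time of onset. Any related grade 5 event qualifies. Every non-fatal criterion needs persistence beyond 4 weeks, while section 7.1 sets a 21-day cycle.
- Section 10.4, footnote 1, requires expedited reports of "Serious adverse events that occur more than 30 days after the last administration of investigational agent/intervention" when they are at least possibly related and meet its grade criteria. Sections 10.52 and 10.6132 do the same for related deaths beyond 30 days.
- Sections 4.1, 4.2 and 13.4 schedule adverse event assessment every 3 months in observation, for up to a year.

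**The concern.** The stopping rules are the only formal, numerical safety trigger that runs through the whole trial. On a plain reading they count an event only if it arises during a cycle of the regimen. A patient whose related DLT or death begins after the last cycle stays in the denominator as a treated patient and adds nothing to the numerator. The proportion compared with 4/12, 2/6 and 30% then comes out too low for a type of toxicity that the protocol itself says may be delayed.

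The data are not lost. They are collected and reported, but section 16.52 does not say that they count. At stake are suspension of accrual in Arm C and the halt on new combination starts in Arms A and C. The Arm A and Arm B schemas record closure to accrual in April 2016 and April 2017, so an accrual suspension no longer has any effect there.

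**Working it through.** **Plan's own figure.** The documents give no operating characteristics for the section 16.52 rules, so there is nothing to reproduce.

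**Step 1: the texts side by side.**

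- Section 16.52 ties events to cycles. Section 16.4 sets no onset limit. Sections 9.9b and 15.191 place some onsets months after the last dose.
- A grade 4 toxicity that begins in a last 21-day cycle can meet its more-than-4-week criterion only after day 28, when that cycle is over. Section 16.52 does not say whether it counts.
- A related death that begins well after the last cycle is a DLT under section 16.4 and reportable under section 10.52, but on the plain reading it is outside the count.

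**Step 2: size, as illustration.**

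Inputs from the plan: thresholds of 4 in the first 12 then 30% (single agent), and 2 in the first 6 then 30% (combination); 20 patients planned in Arm C and 23 evaluable in each of Arms A and B (section 16.12).

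Inputs assumed: true DLT rate p; share f of DLTs with onset after the last cycle; 20 patients starting the combination; every counted event known at once, in enrolment order.

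If late events are left out, the counted rate is p × (1 − f). With p = 0.40 and f = 0, 0.25, 0.50, this is 0.40, 0.30, 0.20.

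First look only, exact binomial:

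- P(at least 4 of 12) = 0.775, 0.507, 0.205.
- P(at least 2 of 6) = 1 − (1 − q)^6 − 6q(1 − q)^5, where q is the counted rate. At q = 0.40: 1 − 0.047 − 0.187 = 0.767. At 0.30 and 0.20: 0.580 and 0.345.

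Whole rule, exact patient-by-patient recursion. The rule fires in the early block once the fixed count is reached, and afterwards at any n where the count is at least 0.30n. For the single-agent rule that means 4 events at n = 13, 5 at 14–16, 6 at 17–20 and 7 at 21–23.

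| Rule | True DLT rate | f = 0 | f = 25% | f = 50% |
|---|---|---|---|---|
| Single agent, by n = 20 (Arm C) | 40% | 0.914 | 0.686 | 0.309 |
| Single agent, by n = 23 | 40% | 0.930 | 0.710 | 0.321 |
| Single agent, by n = 23 | 30% | 0.710 | 0.422 | 0.146 |
| Combination, by n = 20 | 40% | 0.945 | 0.785 | 0.474 |
| Combination, by n = 20 | 30% | 0.785 | 0.562 | 0.296 |

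With a late share of only 10% and a 40% rate, the single-agent figure by n = 23 is 0.867 against 0.930.

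The direction does not depend on the assumptions: leaving events out of the numerator with the same denominator can only lower the chance of firing. The size depends on them entirely. The f = 0 column is also optimistic, because an event that starts months after a last dose may surface after accrual has ended.

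**The case against.** A reader might infer that late DLTs and deaths can never reach the trigger. The documents do not support that, for four reasons.

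1. **The phrase may assign events and not cut them off.** It follows directly on the mention of study treatment. The rule looks at events at any time, the section 16.52 heading splits evaluation by regimen, section 16.328 makes the same split, and the DLT definition is untimed. A strict cut-off also fits poorly with criteria that last longer than a cycle. This stands as a possible reading. Against it, the heading already separates the regimens, so the phrase would then add little. Both readings are open, and that is itself a defect in a stopping rule.
2. **Some late single-agent effects are caught elsewhere.** Patients in Arms A and C who progress, or are stable at month 3, may add a signal inhibitor while MK-3475 continues (section 7.3). A delayed effect appearing then falls in combination cycles, under the 2-of-6 rule. This stands. It weakens any claim that the shortfall is greatest in patients who stop single-agent treatment early for progression.
3. **The window is not always 3 weeks.** One might infer that counting stops about 21 days after the last dose, with half the drug still present. By the 22-day half-life in section 15.15, 0.5^(21/22) = 0.52 remains at day 21. But section 8.1 lets the interval grow to 8 weeks and section 7.1 lets the longer interval become the cycle, which gives 0.5^(56/22) = 0.17. The half-life argument is therefore not general.
4. **Other safeguards exist.** The study team may suspend accrual before a rule is crossed and may adjust the rule at any time, the DSMB reviews safety at least twice a year, and related late deaths are reported within 24 hours. These soften the gap without closing it. They are discretionary or periodic, and the suspension clause concerns unexpected profiles, whereas the protocol expects delayed immune events. The separate review of grade 4 and 5 events covers those judged unrelated or unlikely, which is a different set.

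**Conclusion.** The point holds in a limited form. As worded, section 16.52 need not count a related DLT or grade 5 event with onset after the last cycle. The text admits two readings, so two analysts could reach different counts from the same data. It does not follow that such events are always excluded, or that they go unseen.

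The practical reach is Arm C accrual and further combination starts in Arms A and C. On an assumed 40% true DLT rate, leaving out an assumed quarter of DLTs lowers the chance that the single-agent rule fires in Arm C from 0.91 to 0.69, and leaving out half lowers it to 0.31. For the combination rule the figures are 0.945, 0.785 and 0.474. Treatment can run for 12 to 24 months, so much of the onset time falls within cycles and the true late share may be small; the documents do not give it. The change should be made because the text is ambiguous and the repair is cheap, not because these probabilities are established.

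**What to change.** Reconcile section 16.52 with sections 9.9b, 10.4 footnote 1, 10.52 and 16.4. In both rules, reword the reference to cycles so that it assigns an event to a regimen and does not limit its onset. Specifically:

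- Count any event that meets section 16.4 and is at least possibly related, including events reported under section 10.4 footnote 1 and section 10.52.
- Assign each event to the last regimen received before its onset. A toxicity that begins in a last cycle and meets the 4-week criterion later then counts toward that regimen.
- State the length of any post-treatment window, and whether a related death beyond it still counts. That length is for the study team to set. It should be an explicit period, because section 10.62 leaves late events after active monitoring to the forms instructions and so gives no defined end of collection.

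The thresholds need not change.

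The cost is a sentence or two and no new data collection. For patients who go straight to event monitoring there are no observation visits, so their late events will reach the count through expedited and late-event reporting. The downside is that a suspension or halt may come earlier or more often; counting more events over the same denominator cannot make it come later.
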